# 1 BACKGROUND AND RATIONALE

## 1.1 General Introduction

Recent outbreaks of Ebola and MERS, and in the trend of growing threat of MRSA and multi-drug resistant pathogens, it is clear that we need a new means of countering the infectious threat – even the US, EU, and Korean hospitals with the latest facilities has failed to stop the spread of these pathogens inside their wards. This novel “Harmless UV Light,” operating within the “Safe Zone Wave Length,” will be a disruptive technology to counter the growing threats of infectious diseases, such as multi-drug-resistant bacteria and also viruses such as Ebola, MERS and new type Influenza. It will be a disruptive device in that it aims to be applied to fast, effective and labor-free disinfection of living environments, such as hospital wards, airports, and other public spaces to stop the spread of pathogens. This research is the first human clinical trial using this device that will spearhead the development of this technology, providing the key starting clinical data which would be the lead to development for a wider range of indications and markets. Successful proof of concept will lead to the next stage collaboration of larger scale clinical trials, and trials targeting wider range of indications and markets, at NUHS. This will bring strong opportunities for joint application to Japan (AMED) and Singapore government grants, and joint marketing strategy to Asia. Pressure sore has been selected as the first target disease because of (1) its large need for effective treatment from increasing prevalence in aging society, (2) its rather uniform pathology based around bacterial infection, and (3) easiness to quantitatively measure the degree of bacterial infection and the rate of healing.

The device to be used in this study is a UV-Photo Disinfection device. Safe zone UV (SUV) irradiation (222 nm) to be used for the study will be manufactured by Ushio Inc. It is currently not in use in humans. UV light is a well-established anti-microbial modality, effective both against bacteria and viruses

## 1.2 Rationale and Justification for the Study

### 1.2.1 Rationale for the Study Purpose

Previous preliminary work by Ushio Inc. and Columbia University (Industry) in 2013, Buonanno et.al, reported that 190nm-230nm UV light is as efficient as conventional germicidal lamps for inactivating MRSA, but is far safer in regard to human exposure. UV light at a wavelength of around 200 nm is very strongly absorbed by proteins, so its ability to penetrate biological material is very limited. For example, the intensity of ~200-nm UV light is reduced by half in only about 0.3  $\mu\text{m}$  of tissue, compared with about 3  $\mu\text{m}$  at 250 nm and much longer distances for higher UV wave-lengths. The very short range in biological material of the ~200-nm far-UVC wavelength means that, while it can penetrate and kill bacteria and viruses, it cannot penetrate the cell nucleus of individual human cells – typical human cells range in diameter from about 10 to 25  $\mu\text{m}$ . Buonanno et al showed the experimental result of inactive MRSA by using 207nm excimer lamp. Testing using 254nm,222nm and 207nm lamps in inactivating MRSA was done. 207nm,222nm UV-C lamp were showed to have the same capability of germicidal UV lamp(254nm) for inactivating bacteria and viruses.

As for in-vitro safety data, there are two studies performed. Mutation of DNA did not happen in both cases of 207 and 222nm irradiation. As for in-vivo safety data, preliminary study was performed in hairless mouse skin. The hairless mice were exposed to monochromatic 207-nm

UV by a filtered KrBr excimer lamp and a standard germicidal lamp UV (254 nm). The mice were sacrificed and dorsal skin sections were analyzed in terms of induction of cyclobutane pyrimidine dimers (CPD), and induction of pyrimidine-pyrimidone 6-4 photoproducts (6-4 PP). The epidermal layer thickness of dorsal skin exposed to 207 nm light was not statistically different from controls, by contrast, that was generated by 254 nm light resulted in a 2.7 fold increase. Exposing to 254 nm light resulted in a dramatic increase versus controls in the percentage of premutagenic skin lesions CPD and 6-4 PP in epidermal cells, whereas the tissue exposed to the same fluence of 207 nm UV light showed no statistically significance increase of these epidermal lesions relative to the controls. Minimal erythema dose test (MED) of healthy volunteer skin was also performed. It was found the 207 nm and 222 nm MED of the skin is much higher than that of 254nm. The 207nm light did not display any sign of erythema up to 50mJ/cm^2, although the MED of 254nm is 10mJ/cm^2. For the 222nm, erythema did not occur up to 300mJ/cm^2.

This study is a first in human proof of concept that the 222nm UV light is as effective in human subjects as compared to the in-vitro studies mentioned above.

## **2 HYPOTHESIS AND OBJECTIVES**

### **2.1 Hypothesis**

UV light is a well-established anti-microbial modality against bacteria and viruses - yet conventional 254nm UV light is associated with raised risks of skin cancers and cataracts that limit its use. A new UV lamp by Ushio Inc. emits selected wave length of 222nm that has demonstrated in previous in vitro and in vivo studies, to cause significantly less harm to human cells, while maintaining major disinfecting capabilities.

### **2.2 Primary Objectives**

This proof-of-concept study aims to demonstrate the efficacy of the “Safe-Zone” 222nm Ultraviolet-C (UVC) light to manage bacterial infection in pressure sore and accelerate healing of pressure sore by removing bacterial infection which is known to play a major role in slowing the healing of these wounds.

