### **4 STUDY DESIGN**

20 patients with presence of pressure sore estimate at 2 cm X 2 cm or bigger will be recruited in NUH for a period of 2 years. Using Ushio's prototype, narrow-band 222 nm UV light will be irradiated onto selected pressure sore area for 90 seconds, 2 times per week over 2 weeks duration after the wound is cleaned and dry. A plastic sheet with a hole of 2 cm X 2 cm will be used to guide the UV Light positioning on the pressure sore and to ensure that irradiation is shielded and will be blocked to only target at the selected pressure sore area. The UV light will be held at 1cm above the pressure sore. Wound culture and sensitivity before and immediately after each UV treatment will be done to determine if there is any decrease in bacteria count. Result can be used to determine the presence of wound infections prior to/after the UV treatment. Secondary to that, pictures of the selected pressure sore area before and after UV treatment will be taken and healing rate will be measure using Pictzar program. Healing rate will be estimated by scaling the size, the color, the edge form and the elasticity by using a color camera until the sores heal up to 50% to the full recovering to see if there is any decrease in wound size. After the trial, researchers will suggest improvements to the device from clinical perspective which will lead to mass production types. Successful result will be followed by a

larger scale clinical test at NUHS with joint application to Japan (AMED) and Singapore government grants, and joint marketing strategy to Asia

A more detailed description of the process of sample collection is attached in Appendix 1.

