##### **4.3.2 Study Visits and Procedures**

Using Ushio's prototype, narrow-band 222 nm UV light will be irradiated onto selected pressure sores area for 90 seconds, 2 times per week over 2 week duration after the wound is cleaned and dry.

No additional hospital visits will be required.

Regular wound cleaning / debridement and dressings of the pressure sore will be performed

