## **6.6 Concomitant therapy**

Regular wound debridement and dressing changes will be performed as per regular treatment for pressure sores.

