### Procedure to obtain wound swab samples

1	Consent obtained from patient
2	Wound is exposed
3	Bedside wound debridement is performed 

- Eschar is excised

- Slough removed

4	Irrigation of the wound with 0.9% Normal saline to be performed
5	A photo of the wound using the designated study camera to be taken
6	A Tegaderm with the wound dimensions is fashioned and applied over the wound, exposing the wound bed but covering the wound edges
7	A swab of the wound bed is taken. *
8	One time use pre-made 2x2 headframe is put over the UV light device
9	UV light therapy is commenced over the wound bed 1 cm from the wound bed for 90sec at 6mJ/second for a total of 540 mJ 

- The device is to be held directly above the wound bed at right angles

10	A swab of the wound bed is taken immediately after UV light therapy *
11	The Tegaderm is removed
12	A photo of the wound using the designated study camera to be taken
13	The wound is dressed with Allevyn dressing

\*Wound swab samples to be taken with sterile wound swab tip.

The samples will be stored in a sterile dry tube and send to the Microbiology Lab at NUH

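### The aim of faster healing has no comparator in this single-group trial; as a minor second point, the swab sites are not tied to the irradiated area

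*Protocol*

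**What the plan says.** **Healing.** Section 2.2, headed as the primary objectives, aims to demonstrate the efficacy of the light "to manage bacterial infection in pressure sore and accelerate healing of pressure sore by removing bacterial infection". Section 4 describes one group of 20 patients, each irradiated twice a week for two weeks (four sessions). Section 4.1 marks randomisation and blinding as not applicable. Wounds are photographed and measured "to see if there is any decrease in wound size". Routine care continues for everyone. Section 4.3.2 says "Regular wound cleaning / debridement and dressings of the pressure sore will be performed", and section 6.6 says "Regular wound debridement and dressing changes will be performed as per regular treatment for pressure sores". No untreated group, untreated wound area, run-in rate or historical rate is named. Section 1.2.1 compares only with laboratory studies, which supply no healing rate.

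**Swabs.** Section 4 states: "Wound culture and sensitivity before and immediately after each UV treatment will be done to determine if there is any decrease in bacteria count". In Appendix 1, steps 7 (before UV) and 10 (straight after UV) open with the same words, "A swab of the wound bed is taken", and neither fixes a site. Step 6 applies a film cut to the size of the wound, leaving the bed open. At step 8, "One time use pre-made 2x2 headframe is put over the UV light device". Section 4 also describes a plastic guide sheet with a 2 x 2 cm hole, but Appendix 1 does not say when it is placed.

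**What follows.** Section 4 says "Successful result will be followed by a" larger clinical test, with joint grant applications.

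**The concern.** To accelerate healing is to make it faster than it would otherwise have been. The protocol measures each wound against its own starting size, while care intended to heal the wound runs alongside. Shrinkage could therefore be reported as meeting a primary aim when it says nothing about the lamp's contribution.

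The before-and-after swabs are a better comparison, because routine care falls outside the interval: debridement and irrigation (steps 3 and 4) precede the first swab, and the dressing (step 13) follows the second. Two sampling effects remain. Where the swabs overlap, bacteria removed by the first are missing from the second. Where the sore is larger than 2 x 2 cm, the second swab may pick up bed that was never irradiated. The first effect inflates the apparent fall and the second shrinks it. Section 4 sets no minimum size for a decrease in count, so small falls matter to how the result is read.

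**Working it through.** The protocol has no figure to reproduce: section 9.1 gives no sample-size derivation. From the documents come n = 20, four sessions, the 2 x 2 cm irradiated area and the step order. Every removal share, overlap, SD and shrinkage rate below is assumed.

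**1. Healing.** Suppose the lamp is inert and routine care alone shrinks area by a mean m with SD s (percentage points). For a one-group test against zero (n = 20, two-sided 5%), the chance of declaring a decrease is the upper tail of a noncentral t with 19 df and noncentrality (m/s) × √20. For m = 10 and s = 20 the noncentrality is 0.5 × 4.47 = 2.24.

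| Mean shrinkage | SD 20 | SD 30 | SD 40 |
|---|---|---|---|
| 10% | 56% | 29% | 19% |
| 20% | 99% | 81% | 56% |

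More patients would raise these figures, not lower them, because the test asks whether wounds shrank and not whether UV made them shrink faster.

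**2. Depletion by the first swab.** If it removes a share f, and a share o of the second swab overlaps it, the apparent fall with an inert lamp is −log10(1 − f × o). For f = 0.5 and o = 1 this is −log10(0.5) = 0.30.

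| Removal f | 10% | 20% | 30% | 50% | 70% | 90% |
|---|---|---|---|---|---|---|
| Full overlap | 0.05 | 0.10 | 0.15 | 0.30 | 0.52 | 1.00 |
| Half overlap | 0.02 | 0.05 | 0.07 | 0.12 | 0.19 | 0.26 |

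With no overlap the shift is zero.

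**3. Dilution by un-irradiated bed.** If a share u of the second swab comes from outside the irradiated area, and counts were uniform before UV, a complete kill inside the area shows a fall of at most −log10(u). For u = 25, 50 and 75% this is 0.60, 0.30 and 0.12 log10.

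**4. What depletion alone would do to a test.** Take a swab SD of 0.5 log10. A patient's four-session mean difference then has SD √(2 × 0.5² / 4) = 0.354. With 20 patients and a paired two-sided 5% test, an inert lamp would show a decrease in:

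- 4.5% of trials (10% removal) and 13% (30% removal) at half overlap;
- 8% and 46% at full overlap.

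Without depletion the figure is 2.5%. Adding a between-patient SD of 0.3 lowers these to 4%, 9.5%, 6% and 29%. Dilution does not enter here, because an inert lamp leaves no kill to dilute. With a working lamp, both effects act.

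**5. Scale.** Section 2.3.2 cites 4 to 5 logs of kill for conventional lamps. Even 90% removal at full overlap gives only 1.0 log10.

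**6. Precision if the swabs are taken from separate halves.** The 95% half-width is t(0.975, 19) × √((2 × 0.5² + 2 × h²)/4 + b²)/√20, where h is the SD between halves and b the between-patient SD. With t = 2.093:

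| | h = 0 (same site) | h = 0.3 | h = 0.5 |
|---|---|---|---|
| b = 0 | 0.17 | 0.19 | 0.23 |
| b = 0.3 | 0.22 | 0.24 | 0.27 |

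**The case against.** **An outside rate could be the comparator.** The SAP is not at hand, and it could name a reference healing rate in advance. This stands as a limit: a reader might infer that the healing aim could never be met at any sample size, and the documents do not support that. What they show is that the protocol names no such rate and that its stated criterion, any decrease in size, does not need one.

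**It is a proof of concept, and healing ranks second.** A single group is acceptable for this purpose, and section 4 does place the photographs after the cultures. But section 2.2 lists healing among the primary objectives. The claim needs to change; a control arm is not required.

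**The swab bias may run against the lamp.** This stands. Sores may exceed 2 x 2 cm, so dilution can be as large as depletion. A reader might infer that swabbing can only flatter the lamp; the documents do not support that.

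**The target area is partly marked already.** This also stands in part. For a sore close to 2 x 2 cm, the step 6 window largely is the target. For a larger sore it outlines the wound, not the irradiated part.

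**Splitting the swabs buys little.** Small falls remain hard to interpret afterwards, because drying and elapsed time differ between the swabs and there is no un-irradiated pair. Appendix 1 irrigates at step 4 and lists no drying step, although section 4 has the wound dry before UV. The main gain is that both swabs stay inside the irradiated area; removing the overlap comes second.

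**A multi-log fall may not be observable.** Obviously infected wounds are excluded (section 3.4) and the bed is debrided and irrigated first. This is plausible, but no baseline count is given.

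**Conclusion.** The healing point holds and should be fixed. With one group, routine care for all and no named comparator or reference rate, a decrease from baseline cannot show acceleration. This rests on the protocol's text alone; the 19 to 56% and 56 to 99% figures only illustrate it under assumed shrinkage and SDs.

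The swab point is minor. Depletion can mimic a fall of about 0.02 to 0.5 log10 at an assumed 10 to 70% removal and half to full overlap. Dilution can cap a complete kill at 0.60 to 0.12 log10 at assumed un-irradiated shares of 25 to 75%. The net direction is unknown because the documents fix none of these shares. A reader might go further and infer that any fall in count would be an artefact. That does not follow: depletion cannot produce a fall of several logs, a paired analysis deals with chance variation between swabs, and no debridement or dressing step falls between them.

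**What to change.** **Healing (should be fixed).** In section 2.2, replace the aim of accelerating healing with *describe wound-area change under UV plus standard care*. In section 4, state that a decrease in wound size will not be read as faster healing. This is wording only; the cost is a weaker healing claim.

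**Swabs (minor).** In Appendix 1, define the 2 x 2 cm target area before step 7 and say where the section 4 guide sheet comes in the sequence. Take both swabs only inside that area, one half before UV and the other half after, with the side chosen at random each session. The cost is a marking step, a list of sides, half the area per swab and a somewhat wider interval: half-width about 0.17 to 0.19–0.23 log10 at the assumed SDs, or 0.22 to 0.24–0.27 with between-patient SD 0.3. No extra patients, visits or swabs are needed.

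**Reporting.** State that drying and elapsed-time effects between the swabs remain uncontrolled, so a small fall alone will not be reported as demonstrated efficacy. This limits what a small fall can support when the larger trial is decided.

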### **2.3 Potential Risks and Benefits:**

#### **2.3.1 Potential Risks**

The downside to the more widespread use of UV radiation in these contexts is that in most wavelengths it is a human health hazard, being both carcinogenic and cataract genic

#### **2.3.2 Potential Benefits**

UV light is a well-established anti-microbial modality, effective both against bacteria and viruses. Studies of surgical wound irradiation with conventional germicidal UV lamps have shown great promise, with UV doses corresponding to 4 to 5 logs of MRSA cell kill, resulting in significant decreases in SSI rates, both of which are extremely important to improved pre-surgical skin

disinfection, and to the effective treatment of infected serious wounds, such as infected diabetic ulcers.

### **3 STUDY POPULATION**

#### **3.1 List The Number and Nature of Subjects to be Enrolled.**

20 patients with presence of pressure sore estimate at 2 cm X 2 cm or bigger will be recruited in NUH for a period of 2 years

#### **3.2 Criteria for Recruitment and Recruitment Process**

Criteria for recruitment will be all patients with the presence of pressure sores estimating a size of 2 x 2 cm or bigger. The patient will be recruited during consultation either in the ward or clinic by the PI and study team members

#### **3.3 Inclusion Criteria**

All patients with pressure sore estimate at 2 cm X 2 cm or bigger will be recruited in NUH for a period of 2 years. The lower age limit of recruitment is 21 and the upper age limit of recruitment is 100 years old.

#### **3.4 Exclusion Criteria**

Patient who has pressure sore exposing bone  
Patient who are beyond the age limits  
Patient who is septic  
Patient with obviously infected wound / pus in the wound  
Patient who is pregnant.

#### **3.5 Subject Replacement**

N.A.

### **4 STUDY DESIGN**

20 patients with presence of pressure sore estimate at 2 cm X 2 cm or bigger will be recruited in NUH for a period of 2 years. Using Ushio's prototype, narrow-band 222 nm UV light will be irradiated onto selected pressure sore area for 90 seconds, 2 times per week over 2 weeks duration after the wound is cleaned and dry. A plastic sheet with a hole of 2 cm X 2 cm will be used to guide the UV Light positioning on the pressure sore and to ensure that irradiation is shielded and will be blocked to only target at the selected pressure sore area. The UV light will be held at 1cm above the pressure sore. Wound culture and sensitivity before and immediately after each UV treatment will be done to determine if there is any decrease in bacteria count. Result can be used to determine the presence of wound infections prior to/after the UV treatment. Secondary to that, pictures of the selected pressure sore area before and after UV treatment will be taken and healing rate will be measure using Pictzar program. Healing rate will be estimated by scaling the size, the color, the edge form and the elasticity by using a color camera until the sores heal up to 50% to the full recovering to see if there is any decrease in wound size. After the trial, researchers will suggest improvements to the device from clinical perspective which will lead to mass production types. Successful result will be followed by a

larger scale clinical test at NUHS with joint application to Japan (AMED) and Singapore government grants, and joint marketing strategy to Asia

A more detailed description of the process of sample collection is attached in Appendix 1.

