## **11 QUALITY CONTROL AND QUALITY ASSURANCE**

The investigators and the collaborators in the study team will be responsible for the safety and accuracy of the data.

The electronically stored data will include minimal necessary information mainly wound sites, sites where culture is taken, time where culture is taken, result of culture test, some demographic data and details of treatment implemented.

It will be reviewed by the PI on a monthly basis. Any significant findings will be recorded as well.

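### The fall in bacteria count that Section 4 sets out to show is not secured: no quantitative culture, unit or stored count is specified, and in larger wounds the swab can include tissue the UV did not reach

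*Protocol*

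**What the plan says.** **The test and its purpose.** Protocol Section 4: "Wound culture and sensitivity before and immediately after each UV treatment will be done to determine if there is any decrease in bacteria count". The next sentence gives the same result a second, yes/no use: "Result can be used to determine the presence of wound infections prior to/after the UV treatment". Healing comes after it: "Secondary to that, pictures of the selected pressure sore area before and after UV treatment will be taken". The objective in Section 2.2 has both parts: "to manage bacterial infection in pressure sore and accelerate healing of pressure sore by removing bacterial infection".

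**The rationale.** Section 1.1 gives as one reason for choosing pressure sores the "easiness to quantitatively measure the degree of bacterial infection and the rate of healing".

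**Sampling.** Section 4 refers to Appendix 1 for detail of sample collection. There the wound is debrided and irrigated (steps 3 and 4). A transparent dressing shaped to the wound's dimensions is applied so that the bed stays open (step 6). The bed is swabbed (step 7), irradiated (steps 8 and 9) and swabbed again (step 10). Only then is the dressing removed (step 11). The procedure ends: "The samples will be stored in a sterile dry tube and send to the Microbiology Lab at NUH".

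**The field.** Section 4 confines irradiation to a 2 cm x 2 cm opening. Sections 3.1 and 3.3 admit wounds of that size or larger.

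**The record.** Sections 11 and 12.2 list the bacteriological data item only as "result of culture test". Section 8.1 has one person take all pictures and samples.

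**The concern.** There are two gaps between the outcome and the data that would be collected.

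First, a fall in count needs a number at each time. Culture and sensitivity, as usually understood, reports which organisms grew and what they are susceptible to. It gives a count only if a quantitative or semi-quantitative method is requested, and the protocol requests neither. If results came back as growth or no growth, a lamp that killed most but not all bacteria could leave both swabs positive.

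Second, the area swabbed is not tied to the area irradiated. In a wound larger than the 2 x 2 cm opening, a swab of the whole exposed bed mixes treated and untreated surface, so the before/after difference shrinks even if every step is followed exactly.

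Neither gap can be closed at analysis. No statistical plan can recover counts that were never made, or separate irradiated from unirradiated bacteria on one swab.

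**Working it through.** Sections 9.1 and 9.2 are marked not applicable, so there is no planned figure to reproduce.

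**1. Is a count specified anywhere?**

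| Place | What a count would need | What is there |
|---|---|---|
| Section 4 | quantitative method, unit | culture and sensitivity; no unit |
| Appendix 1, steps 7 and 10 | stated swab area and technique | a swab of the wound bed |
| Appendix 1, closing note | request for counting | dry tube to the laboratory |
| Sections 11 and 12.2 | count, detection limit | the culture result |

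Nothing rules a count out, and nothing secures one.

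**2. Number of swabs.** 2 sessions a week x 2 weeks = 4 sessions. 4 x 2 = 8 swabs per patient. 20 x 8 = 160 swabs at most, or 80 before/after pairs.

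**3. What growth/no growth would show.** All inputs here are assumptions; the protocol gives none. Let log10 CFU before UV be normal with mean m and SD s, let the detection limit be L = 1, and let UV remove k logs. The share of swabs turning from positive to negative is

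Φ((L + k − m)/s) − Φ((L − m)/s).

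- m = 5, s = 1, k = 2: Φ(−2) − Φ(−4) = 0.0227, about 2%, or 0.5 of 20 patients with one pair each.
- m = 5, s = 1, k = 4: Φ(0) − Φ(−4) = 0.500, or 10 of 20.
- m = 3, s = 1, k = 2: Φ(0) − Φ(−2) = 0.477, about 48%, or 9.5 of 20.
- m = 6, s = 1, k = 2: Φ(−3) − Φ(−5) = 0.0013, or 0.03 of 20.
- m = 4, s = 1.5, k = 2: Φ(−0.67) − Φ(−2) = 0.230, or 4.6 of 20.

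In the first case the chance of seeing no conversion at all is (1 − 0.0227)^20 = 0.63 with one pair per patient. With all 80 pairs, if they were independent, it is (1 − 0.0227)^80 = 0.16. The true value depends on the correlation within patients.

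**4. Dilution by unirradiated tissue.** The field is 2 x 2 = 4 cm². Assume bacteria are spread evenly over a wound of area A cm² and the swab samples all of it evenly. The fraction surviving on the swab is then

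1 − (4/A)(1 − 10^−k).

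For k = 2:
- A = 4 (the minimum size): 0.01, so the full 2 logs are seen.
- A = 8 (assumed): 1 − 0.5 x 0.99 = 0.505, a fall of 0.30 log.
- A = 16 (assumed): 1 − 0.25 x 0.99 = 0.7525, a fall of 0.12 log.

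If the operator happens to swab only inside the field, there is no dilution. The protocol leaves this open.

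**The case against.** A reader might infer that the plan orders the wrong test and that the count cannot be obtained. The documents do not support that. Section 4 itself says the culture is done to look for a fall in count. A count is also a culture result, so the storage wording in Sections 11 and 12.2 is neutral. Appendix 1 covers how swabs are obtained, and bench steps such as dilution and plating may sit in a laboratory procedure. What stands is narrower: the protocol does not ask for the count.

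A reader might also infer that sampling is uncontrolled. It is not. One person takes all samples, and the mask stays in place from before the first swab until after the second, so both come from the same exposed bed. This limits operator and site variation. It does not help with dilution, because the mask follows the wound and not the irradiated field.

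A third tempting reading is that the trial would probably report no effect. That depends on the assumed kill and baseline. Section 2.3.2 speaks of "UV doses corresponding to 4 to 5 logs of MRSA cell kill", though for conventional lamps, and Section 1.2.1 reports that 222 nm inactivates as well as 254 nm. With kills that large, many swabs would convert at a mean of 5. Excluding obviously infected wounds (Section 3.4), and debriding and irrigating first, may also lower the baseline. The size of the loss is therefore not established.

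Finally, no item is labelled a primary endpoint. That the count leads is inferred from its position in Section 4 and from the words that place healing second.

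**Conclusion.** The concern holds as a failure to secure the measurement. The protocol wants a change in count but does not specify a quantitative culture, a unit or a stored count, and its sampling steps can mix irradiated and unirradiated surface in wounds above 2 x 2 cm. The mixing biases the change toward no effect. The protocol does not show how many wounds this would affect.

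The illustrative loss under growth/no-growth reporting is wide. A 2-log kill would convert anywhere from almost no swabs to about half of them, depending on the assumed baseline, and nothing says the laboratory reports in that form. The figures show that a real effect could be missed, not that it would be. Should-fix.

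**What to change.** - **Section 4:** state quantitative culture of both swabs, reported as log10 CFU per stated area.
- **Appendix 1, steps 7 and 10:** take both swabs with the same technique from equal, fixed areas inside the irradiated 2 x 2 cm field. Non-overlapping areas are preferable, for example two halves with alternation of which is swabbed first. The first swab itself removes bacteria, and with no control arm (Section 4.1 is marked not applicable) a fall caused by swabbing the same spot twice would be credited to UV.
- **Section 11:** store the count and the detection limit.
- **If counting is not feasible:** restate the outcome in Section 4 as a semi-quantitative grade or growth/no growth, so that the claim matches the data.

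The cost is protocol wording and modest extra laboratory work on at most 160 swabs already planned. Splitting the field halves the area sampled by each swab and brings in variation between the halves; alternating the order keeps that from becoming a systematic bias. The change has to be made before samples are taken, since the counts cannot be recovered later.
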